1.0 Objectives

1.1 **Purpose:** We propose a 100-participant randomized controlled 2-arm parallel trial which employs a metagenomic approach to examine how 8 weeks of supervised moderate-intensity treadmill walking exercise (MWE)^{1,2} for 30-45 min 3 times/week alters the gut microbiome, serum SCFAs, and the cardiometabolic profile, body weight, and body composition of individuals 30-64 years old who are overweight or obese and have PreD.

Aim 1: Compare the effect of 8 weeks of MWE vs. control on shifts in the gut microbiome of overweight or obese individuals with PreD. **H1:** Gut microbial diversity and functional capacity (specifically, genes relevant to SCFA production) will increase improve after 8 weeks in the experimental group vs. control.

Aim 2: Compare the effect of 8 weeks of MWE vs. control on changes in serum SCFAs. **H2:** Serum Levels of SCFAs butyrate, acetate, and propionate will increase after 8 weeks in the experimental group vs. control.

Aim 3: Use formal mediation methods to estimate the proportion of MWE-induced changes in participants' cardiometabolic profiles, body weight, and body composition that are mediated by changes in the gut microbiome and/or serum SCFAs. **H3:** MWE-induced changes in the gut microbiome and serum SCFAs will partly explain changes in participants' cardiometabolic profile (e.g., blood lipids, fasting insulin/glucose, blood pressure, waist circumference), body weight, and body composition.

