3.0 Study Endpoints/Events/Outcomes

3.1 **Primary Endpoint/Event/Outcome:** Expanded data collection procedures for our primary and secondary outcomes are available in Section 5.2. We have two Primary Outcomes. The first primary outcome is changes to the gut microbiome, assessed via metagenomic sequencing, from pre- to post-intervention (**Specific Aim 1**). The Shannon Index—a measure of microbial community diversity with good reproducibility (ICCs>0.50)⁵⁶—will be our primary indicator for changes in gut microbiota composition, and will be assessed at baseline, and following the 4th and 8th weeks. The second primary outcome is serum SCFA levels. Participants will undergo fasted blood draws to assess serum SCFA levels (**Specific Aim 2**). This work will be performed using the Metabolon pipeline.⁵⁷

3.2 **Secondary Endpoint(s)/Event(s)/Outcome(s):** We have several Secondary Outcomes. For **Specific Aim 3** cardiometabolic profiles will be assessed via assays for high-density lipoprotein cholesterol (HDL-C), triglycerides, fasting insulin/glucose, and c-reactive protein (CRP). All blood assays will be conducted by the *UMN Advanced Research and Diagnostic Laboratory* (see ‘Facilities’ document). Blood samples collected will be stored at -80°C prior to batch-processing. Resting blood pressure (BP) will be taken using an Omron Automatic BP Cuff (Omron; Lake Forest, IL), with the average of the last two BP measurements reported. These cardiometabolic indices form the foundation of the ‘metabolic syndrome’,⁵⁹⁻⁶³ and we will form a composite continuous score for cardiometabolic disease risk from HDL-C, fasting glucose, triglycerides, the average of systolic and diastolic BP, and waist circumference. Specifically, z-scores for each biomarker will be calculated and the within-participant average across z-scores computed and referred to as *cardiometabolic disease risk (CMDrisk*; the primary dependent variable for Specific Aim 3). This score has been used in epidemiologic, experimental, and clinical studies.^{62,64-67} Individual components will be described in secondary analyses as needed. We will also measure HbA1c using whole blood analyzed at the UMN Advanced Research Diagnostic Laboratory; the A1cNOW+® device may also be used in a limited capacity to assess validity.⁶⁸ The oral microbiome will be

MEDICAL PROTOCOL (HRP-590)

PROTOCOL TITLE: Exercise and the Gut Microbiome R21

VERSION DATE: 05/11/2022

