15.0 Statistical Considerations

15.1 Data Analysis Plan: Chi-square and independent *t*-tests will evaluate baseline group differences as appropriate. Mediation analyses will also be conducted. We outline our analysis plans in Section 15.3. ⁸⁶⁻⁹²

MEDICAL PROTOCOL (HRP-590)

PROTOCOL TITLE: Exercise and the Gut Microbiome R21

VERSION DATE: 05/11/2022

15.2 Power Analysis: Power for Aim 1 is based on analyses using alpha-diversity (Shannon Index) as the primary outcome. Taniguchi et al.⁴⁶, reported a mean \pm SD baseline Shannon Index of 5.7 ± 0.6 which is consistent with preliminary data from gut samples collected by [name] in other recent projects. Given this variance, and with a balanced design of $n=50$ in the experimental and control arms ($N=100$ total), we will have >99% power to detect a 1 unit increase in Shannon Index. Power for Aim 2 is based on changes in serum SCFAs. Our SCFA assays will be performed at Metabolon and our colleagues at Metabolon provided information on mean \pm SD for these outcomes in their lab. They are as follows: acetate= 1806 ± 2500 ng/mL, butyrate= 35 ± 43 ng/mL, and propionate= 50 ± 52 ng/mL. With these distributions, we will have >80% power to detect a difference in SCFA levels between treatment and control groups with a magnitude of at least 50% of 1 SD.

The primary outcome for Aim 3 will be a composite score based on the average of the z-scores for the following 5 biomarkers: HDL-C, fasting glucose, triglycerides, average of systolic and diastolic BP, and waist circumference. The standardized mean \pm SD of this *CMDrisk* z-score in [name] sedentary behavior intervention among 575 participants (Grant #: R01CA198971) is 0 ± 0.7 . This provides 80% power to detect a difference in the *CMDrisk* z-score of 0.4, between intervention and control at the conclusion of the study.

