15.3 Statistical Analysis: Aim 1 analysis: Gut microbiome data, derived via metagenomic sequencing, will be operationalized as described above. In a primary analysis, generalized linear regression models will regress Shannon Index on intervention assignment. The model is formalized as: $E[Y] = \text{intercept} + \beta_1 * A + \beta_2 * C$. $E[Y]$ =expected Shannon value; β_1 =coefficient for intervention arm; β_2 =coefficient for a vector of confounders should this be necessary in our randomized design. Secondary analyses will consider metagenomic features (genes and functional profiles). Any metagenomic features not present at >0.1% relative abundance in at least 10% of samples will be removed. Zero-inflated log-linear generalized linear models with a Gaussian error term will be fitted, with treatment status as predictor, as implemented by the metagenomeSeq Bioconductor package for shotgun metagenomic data analyses.⁹³ The generalized model, per metagenomic outcome, is formalized as: $\log E[Y] = \text{intercept} + \beta_1 * A + \beta_2 * C$. $E[Y]$ =expected normalized sequence count value; β_1 =coefficient for intervention arm; β_2 =coefficient corresponding to the vector of baseline confounders. Total read count is incorporated as an offset term. This analysis will generate a “top list” of genes, gene families, and pathways with altered abundance by intervention assignment. Separate models will

MEDICAL PROTOCOL (HRP-590)

PROTOCOL TITLE: Exercise and the Gut Microbiome R21

VERSION DATE: 05/11/2022

be developed for intervention status predicting week 4 and week 8 outcomes. We will also consider time*treatment status models to incorporate stool sampling at all three timepoints. P-values will be corrected for multiple hypothesis testing using the false-discovery rate as we have done previously with high dimensional data.^{86-92,94-98}

Aim 2 analysis: As with Aim 1, generalized linear regression models will be used. Each of three SCFAs (acetate, butyrate and propionate) will be regressed on intervention assignment. The model is formalized as: $E[Y] = \text{intercept} + \beta_1 * A + \beta_2 * C$. $E[Y]$ =expected SCFA value; β_1 =coefficient for intervention arm; β_2 =coefficient for a vector of confounders.

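### H1 names SCFA-production genes as its functional hypothesis, but section 15.3 pre-specifies no SCFA gene or pathway set and no targeted test

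*Combined protocol and SAP*

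**What the plan says.** Section 1.1 states H1 in two parts, diversity and function. On function it predicts that "functional capacity (specifically, genes relevant to SCFA production) will increase improve after 8 weeks in the experimental group vs. control". This is directional, between arms, at week 8, and about a named class of genes.

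Section 3.1 says the Shannon Index "will be our primary indicator for changes in gut microbiota composition". Section 15.2 follows suit: "Power for Aim 1 is based on analyses using alpha-diversity (Shannon Index) as the primary outcome". No power is given for any functional feature.

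Section 15.3 gives Aim 1 one primary model, which regresses the Shannon Index on arm. Function is handled in secondary analyses. After an abundance filter, a zero-inflated model is fitted to each metagenomic feature, separately for weeks 4 and 8, and the result is a ranked list "of genes, gene families, and pathways with altered abundance by intervention assignment". On multiplicity the plan says: "P-values will be corrected for multiple hypothesis testing using the false-discovery rate". It states neither the FDR level nor which tests form the family.

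**The concern.** The diversity half of H1 has a named endpoint, a model and a power statement. The functional half has none of these. Nothing elsewhere fills the gap: Aim 2 tests serum SCFA levels, and the Aim 3 mediators are beta-diversity and serum SCFAs. No section says which genes or pathways count as relevant to SCFA production, how they combine, or what result would support the prediction.

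SCFA features therefore compete with every other feature in their FDR family, and membership of the SCFA class is settled only when the list is read. At stake is how the functional result can be interpreted, and in particular what it means if no SCFA feature appears. The primary Shannon test is unaffected.

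**Working it through.** **Inputs from the documents.** 50 per arm (sections 10.1 and 15.2). Shannon SD 0.6 and difference 1 unit (15.2). The only SCFA-related planning effect is 0.5 SD, for serum levels (15.2).

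**Assumptions, because the documents give no figure.** Two-sided 5%. Benjamini-Hochberg at q = 0.05. m = 100 to 1,000 independent features, of which 1% to 20% are truly altered. The same standardised effect d for a targeted score and for a single feature. On the size of m, the filter sets only a ceiling: at most 999 features can exceed 0.1% in one sample, and each must do so in 10% of samples, so 999 / 0.10 = 9,990 per profile.

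**Step 1: the plan's own Aim 1 figure.** d = 1/0.6 = 1.667. The noncentrality is d × √(n/2) = 1.667 × √25 = 8.33. Against a critical value of 1.96, power exceeds 99.99%. The stated figure of more than 99% reproduces. It says nothing about functional features.

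**Step 2: one pre-specified test.** Power ≈ Φ(5d − 1.96), since √(50/2) = 5.
- d = 0.5: Φ(0.54) = 70.5% (noncentral t: 69.7%).
- d = 0.566: Φ(0.87) = 80.8% (noncentral t: 80.0%).
- d = 0.8: Φ(2.04) = 97.9%.

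Section 15.2 claims more than 80% at 0.5 SD for serum SCFAs. That reproduces only one-sided (80.4%) and is a separate matter.

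**Step 3: the strictest case for the scan.** If only one feature is altered, its threshold is close to 0.05/m. At d = 0.566 the noncentral t gives 23.0%, 12.1% and 9.0% for m = 100, 500 and 1,000. At d = 0.5 it gives 14.5%, 6.9% and 4.9%.

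**Step 4: the scan when more features change.** Benjamini-Hochberg rejects p ≤ kq/m, where k is the number of rejections, so the threshold loosens as true changes accumulate. Simulated with t statistics, average power per altered feature is:

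| d | Lowest (m = 1,000, 1% altered) | Highest (m = 100, 20% altered) | One targeted test |
|---|---|---|---|
| 0.5 | about 6% | about 33% | 70% |
| 0.566 | about 13% | about 50% | 80% |
| 0.8 | about 61% | about 91% | 98% |

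Hand check of one cell (d = 0.5, m = 100, 20 altered): power of 33% implies 20 × 0.33 = 6.6 true rejections, so k is about 7. The threshold is 7 × 0.05/100 = 0.0035, the critical z is 2.92, and Φ(2.5 − 2.92) = Φ(−0.42) ≈ 34%, in agreement.

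**Sensitivity.** If the 20% attrition in section 10.1 left 40 per arm, one targeted test at 0.5 SD has about 60% power. The scan has about 3% to 23% (normal approximation, m = 100 to 3,000).

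**The case against.** The functional analyses are explicitly secondary, and an FDR-corrected scan is an ordinary choice for secondary metagenomic data. That stands, and it limits the weight of the point. It does not supply the missing definition of the hypothesis that H1 names.

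Several stronger readings are tempting, and the documents do not support them:

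- **That the functional half of H1 can be neither confirmed nor refuted.** H1 names the gene class in advance. An SCFA gene or pathway surviving FDR with a positive week-8 coefficient would be error-controlled support. The weakness lies in a null list and in the undefined class.
- **That no quantity summarises SCFA capacity per person, so a coordinated rise must be missed.** The scan includes pathways, and a pathway abundance already adds up its genes within a sample. What is missing is a pathway named beforehand.
- **That the correction runs over all features.** This is the natural reading, but the family is not stated. Correction within pathways or by time point also fits the text.
- **That power is only 9% to 23% at 0.566 SD.** Those are the Step 3 figures, for one altered feature. Step 4 shows how far power rises when more features change.
- **That retaining more features always makes matters worse.** Under FDR it does so mainly when the added features are null. An SCFA gene removed by the filter has no chance of detection at all.

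The assumption of equal effects for score and feature can also fail either way. For example, if 10 genes each rise 0.3 SD with pairwise correlation 0.2 (assumed values), their standardised mean shifts by 0.3 × √(10/(1 + 9 × 0.2)) = 0.57 SD. If many listed genes do not respond, the score is diluted.

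**Conclusion.** The concern holds in a limited form. The absence of an SCFA gene or pathway set and of a targeted test follows from sections 1.1 and 15.3 and depends on no calculation. The power loss is an inference: the documents give no feature count, feature-level SD, effect size, FDR level or family. Under the assumptions listed, the loss is large at 0.5 to 0.566 SD and modest at 0.8 SD when many features change. The consequence is asymmetric: a surviving SCFA feature would be valid support, while its absence would say little against H1.

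**What to change.** Before any arm-level data are examined:

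1. Fix a list of genes and pathways for butyrate, acetate and propionate production.
2. Compute one score per sample from the data before the 0.1% abundance filter, so that the filter cannot strip its components. State the form of the score.
3. Compare the week-8 score between arms in a linear model adjusted for the baseline score. Name this as the single pre-specified secondary test of the functional part of H1, at two-sided 5%, separate from the FDR scan and not counted as a primary outcome.
4. Label the untargeted list exploratory, and state its FDR level and family.

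The cost is a short table in the analysis plan and one extra model on sequencing data already planned. The downside is that the gene list and the form of the score must be chosen in advance, and a poor choice would dilute the effect.

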assessed using a widely employed salivary testing technique. Briefly, we will ask that participants chew a paraffin tablet (Orion Diagnostica) for 5 minutes after which the participant will be asked to spit into a 50mL tube until 5mL of saliva is collected. We have experience with this non-invasive assessment⁶⁹, with the assessment taking no longer than 5-10 minutes overall and presenting no greater than minimal risk. Other secondary outcomes are necessary to measure to ensure we can properly control for confounding. Dietary composition will be assessed via 3 phone-based dietary recalls during the run-in phase, and again during the final two weeks of the study. We will use these dietary recalls collected during the run-in period to develop personalized 3-day meal plan to standardize individual dietary behavior prior to stool sample collection. Employing dietary recalls at these time points will also allow us to adequately statistically control for participants' dietary changes—changes which, if not controlled, might confound study results.^{70,71} Physical activity will be measured for the duration of the study using the Fitbit Inspire 2 smartwatch that uses accelerometry to measure physical activity metrics such intensity, steps, etc. Finally, anthropometric outcomes will include height, weight, and body composition. These measures, along with the other secondary outcomes aside from PA and Dietary composition, will be measured at the end of the 3-week run-in phase, and at the end of the 4th and 8th study weeks.

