collected. The oral microbiome will be assessed using a widely employed salivary testing technique. Participants will be asked to drool into a 50mL tube until 5mL of saliva is collected. For participants that are having difficulty generating saliva, we will ask those participants chew a small piece of orthodontic wax for 5 minutes and then drool into the 50mL tube. We have experience with this non-invasive assessment⁶⁹, with the assessment taking no longer than 5-10 minutes overall and presenting no greater than minimal risk. Other secondary outcomes are necessary to measure to ensure we can properly control for confounding. Dietary composition will be assessed via 3 phone-based dietary recalls. These recalls will be performed on 2 weekdays and 1 weekend day by trained interviewers. Assessment of diet on multiple days allows us to capture the individual variation in participants' diets.⁷¹ We will use these dietary recalls to develop personalized 3-day meal plan to standardize individual dietary behavior prior to stool sample collection. Although randomization should lead to approximately balanced groups with respect to diet, employing dietary recalls at these time points will allow us to adequately statistically control for participants' dietary changes—changes which, if not controlled, might confound study results.^{70,71} Physical activity will be measured during the duration of the study using the Fitbit Inspire 2 smartwatch. Finally, anthropometric outcomes will include height measured using a Seca stadiometer (Seca; Hamburg, Germany), with weight and body composition measured using the Tanita TBF-300a Body Composition Analyzer (Tokyo, Japan).

To collect blood samples and saliva samples as well as body weight, body fat percentage, and blood pressure, we are proposing to employ the following procedures in the designated settings while following all necessary COVID-19 precautions:

Setting: Baseline, week 4, and week 8 visits will occur in the Epidemiology Clinical Research Center (ECRC). We will follow all UMN, OVPR and ECRC approved guidelines for conducting research during the COVID-19 pandemic.

COVID-19 Screening: Participants will complete the OVPR-approved ECRC COVID-19 phone screener the day prior to their visit. Prior to entering the ECRC, participants will call the study coordinator and complete the screening questionnaire again. Upon entry into the building, study staff will assess the participant's temperature.

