Aim 3 analysis: We will use PROC CAUSALMED (SAS 9.4) to explore **mediation** effects on *CMDrisk*. This regression-based model was developed by Valeri and VanderWeele⁹⁹ and VanderWeele.¹⁰⁰ The predictor variable will be treatment (experimental vs. control) and the outcome will be *CMDrisk*. We will include age, *sex as a biological variable*, race/ethnicity, and PA duration as covariates. Mediation will be tested by adding parameters, *in separate models*, for gut microbiota diversity (8-week change in β -diversity) and serum SCFAs (8-week change in levels of serum SCFAs).

15.4 Data Integrity: All data will be double entered separately by two individuals. Blood and stool sample data will be examined for computational value errors associated with out-of-range variables. All data will be examined for outliers and improbable values. More details provided in section 17.1.

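### The Aim 3 mediation model lists no dietary term and no baseline CMDrisk, and does not date PA duration

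*Combined protocol and SAP*

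**What the plan says.** Section 1.1 sets Aim 3: "Use formal mediation methods to estimate the proportion of MWE-induced changes in" the cardiometabolic profile, body weight and body composition that runs through the gut microbiome or serum SCFAs. Section 15.3 gives the model. Treatment is the predictor and CMDrisk the outcome. The mediators, in separate models, are 8-week changes in β-diversity and in serum SCFAs. The covariates are age, sex, "race/ethnicity, and PA duration as covariates".

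Four other places bear on that list.

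- **Diet.** Section 3.2: "Employing dietary recalls at these time points will also allow us to adequately statistically control for" dietary changes. Section 5.2 repeats it: "employing dietary recalls at these time points will allow us to adequately statistically control for" these changes, described as "changes which, if not controlled, might confound study results". Recalls are taken in run-in weeks 1-2 and in weeks 7-8.
- **Other aims.** The Aim 1 model in section 15.3 has a "coefficient for a vector of confounders should this be necessary in our randomized design", and Aim 2 has a similar vector. The metagenomic model has a "coefficient corresponding to the vector of baseline confounders". Aim 3 has no such open term.
- **Outcome.** Section 1.1 speaks of changes. Section 15.2 powers a CMDrisk difference of 0.4 "between intervention and control at the conclusion of the study". Section 15.3 does not say whether CMDrisk is a level or a change. Sections 3.2 and 15.2 include waist circumference in the score. The definition in section 5.2 omits it, and the visit measures there do not list it.
- **PA.** The Fitbit is worn in the run-in (section 5.2) and for the whole study (section 3.2).

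**The concern.** A mediated proportion multiplies two paths: arm to mediator, and mediator to outcome given arm. Randomisation protects the first path and the total effect. It does not protect the second. Anything that moves both the microbiome or SCFAs and the components of CMDrisk biases the second path unless it is in the model. The protocol itself names dietary change as such a factor, yet the analysis most exposed to it does not list it.

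Leaving out baseline CMDrisk is mainly a loss of precision.

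The undated PA term is a different kind of problem. Run-in PA is a harmless baseline covariate. On-study PA is partly the delivered intervention, so adjusting for it takes away part of the contrast being studied.

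**Working it through.** **1. The plan's own figure.** Inputs from section 15.2: difference 0.4, SD 0.7, 50 per arm. Two-sided alpha 0.05 is assumed, because the plan does not state it. The standardised difference is 0.4/0.7 = 0.571, and the two-sample t-test has 80.8% power (normal approximation 81.5%). The stated 80% reproduces, with no covariate used.

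**2. Baseline CMDrisk.** Adjustment reduces the SD to 0.7 × √(1 − r²), where r is the baseline to week-8 correlation. An unadjusted change score has SD 0.7 × √(2(1 − r)). The documents give no r.

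| r (assumed) | adjusted SD | power, adjusted | power, change score |
|---|---|---|---|
| 0.3 | 0.668 | 84.3% | 66.7% |
| 0.5 | 0.606 | 90.4% | 80.8% |
| 0.6 | 0.560 | 94.2% | 88.6% |
| 0.7 | 0.500 | 97.7% | 95.5% |

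**3. Dietary change.** Suppose dietary change moves both mediator and CMDrisk by k SD and there is no true mediation. The within-arm correlation it creates is k². With N = 100, arm and four listed covariates, Fisher's transformation gives a test statistic centred at atanh(k²) × √(100 − 3 − 5) = atanh(k²) × 9.59.

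- k = 0.2: 0.040 × 9.59 = 0.38, false significance 7%.
- k = 0.3: 0.090 × 9.59 = 0.87, false significance 14%.
- k = 0.5: 0.255 × 9.59 = 2.45, false significance 69%.

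Simulation of the listed model gives 6-7%, 13-16% and 69-72%.

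Adding baseline CMDrisk and run-in diet alone does not help here: simulated rates are 13-15% at 0.3 SD and 73-77% at 0.5 SD. Adding dietary change returns the rate to about 5%. If the recalls measure change with reliability 0.6 (assumed), 7-8% and 27-28% remain. If the link runs through habitual diet instead, baseline CMDrisk plus run-in diet is enough (4.6-5.3%).

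The spurious mediated proportion is a × k² × 0.7/0.4, where a is the arm effect on the mediator in SD. At a = 0.6 this is 4%, 9% and 26% for k = 0.2, 0.3 and 0.5. At a = 0.3 it is half that. Its sign follows the direction of the diet effects, so it can create or hide mediation.

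**4. On-study PA.** The assigned walking is (12 × 30 + 12 × 45)/8 = 112.5 min/week, and at an assumed 85% adherence 95.6. With within-arm PA SD s, the variance of the arm coefficient is inflated by 1 + (95.6/2)²/s².

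- s = 29: factor 3.72, power 32%.
- s = 60: factor 1.63, power 61%.
- s = 100: factor 1.23, power 73%.

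These hold when the effect does not follow minutes walked. Simulation that also varies delivered minutes gives 33-49%, 59-63% and 71-73% for a habitual PA SD of 29, 60 and 100, against 78-80% with run-in PA. If the effect does follow minutes, power is lower: about 20%, 51% and 67% in one simulation. It is about 5.5% if the whole effect runs through total weekly minutes.

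**5. Baseline SCFA.** The SCFA mediator is a change score, so it correlates with its own baseline: −0.5 at an assumed retest correlation of 0.5. If baseline SCFA affects CMDrisk by 0.1, 0.2 or 0.3 SD (assumed) and there is no mediation, a model with baseline CMDrisk but without baseline SCFA gives false significance of about 10%, 23% and 42%. With baseline SCFA it is 5%.

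**The case against.** The wording is softer than a quick reading suggests. A reader might infer that the list is closed and that the plan breaks a firm commitment. The documents do not support that. Section 15.3 says which covariates will be included, not that these are the only ones, and sections 3.2 and 5.2 say the recalls allow control of dietary change. The texts can be read together. Still, Aim 3 names no dietary variable and has no open term, so the analyst would have to choose one after seeing the data.

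A reader might also infer that on-study PA would remove most of the power. That holds only for a narrow spread of habitual activity or an effect that follows minutes. The <100 min/week limit comes from a screening questionnaire, and the documents give no SD for Fitbit minutes.

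It is tempting as well to think that baseline CMDrisk plus run-in diet cures the diet problem. Step 3 shows that it does not when the confounder is dietary change. Nor should baseline mediators be ruled out in general. That reasoning fits a between-sample β-diversity measure, but not serum SCFAs, which have a baseline fasting draw.

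Three further points stand. The personalised 3-day meal plan and the criterion on maintaining habits limit dietary change, although they do not adjust for eight weeks of it. Aim 3 is exploratory and its outcome is secondary. At 0.2 SD the bias is negligible, and when arm does not move the mediator both paths are rarely significant together (at most about 8% even at 0.5 SD).

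**Conclusion.** The point holds as a gap in specification. The absent dietary term, the absent baseline CMDrisk, the undated PA covariate and the unstated form of the outcome can all be read directly from the text. None rests on an assumed value.

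The consequences do rest on assumptions. Confounding by diet matters from about 0.3 SD upward, and mainly when exercise does move the mediator. The power loss from on-study PA ranges from modest to severe with the PA SD. The gain from baseline CMDrisk depends on r.

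The documents do not show that Aim 3 will be biased, and the randomised comparison of arms is not in question unless on-study PA enters the model. They do show that a mediated proportion from the listed model could not be told apart from an effect of diet.

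**What to change.** In section 15.3, Aim 3:

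1. Take week-8 CMDrisk as the outcome and adjust for baseline CMDrisk, computed from the same components at both times. First reconcile sections 3.2 and 15.2 with section 5.2 on waist circumference.
2. Specify PA duration as run-in, pre-randomisation PA.
3. Add one or two run-in dietary variables, named before analysis. For each mediator, report beside this a pre-specified model that also adds dietary change (weeks 7-8 minus run-in). State that only this second model addresses the confounding named in sections 3.2 and 5.2, and that dietary change arises after randomisation and may be affected by arm. State also that mediation cannot be separated from dietary change if the two models differ clearly.
4. Add baseline SCFA to the serum SCFA mediator models, and baseline Shannon Index if an alpha-diversity mediator is used. A between-sample β-diversity change has no such baseline.

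The cost is a few sentences, a few degrees of freedom and one extra model per mediator. The data are already collected, apart from waist. Some confounding will remain if the recalls measure dietary change with error.
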